Statistical tables will be generated using SAS version 9.4 or higher. Disposition of all randomized subjects will be summarized by treatment and listed for each subject. Demographic and baseline characteristics will be listed and summarized for the safety population using descriptive statistics. Each subject's exposure to study drug will be listed. Adverse events will be coded using a standardized Medical Dictionary for Regulatory Activities (MedDRA), Version 23.0 or higher. Prior and concomitant medications will be coded using the World Health Organization (WHO) Drug Enhanced Dictionary (March 2020 or later). Tabulations will be prepared including all AEs and all AEs by relationship and severity using Common Terminology Criteria for Adverse Events Version 5.0 [CTCAE v5]. Adverse events resulting in early termination and events meeting regulatory criteria for seriousness will also be tabulated separately. By subject listings of all safety data and concomitant medication use will be generated.

This study will be conducted in accordance with the guidelines of Good Clinical Practices (GCPs) including archiving of essential documents.

Table 1: Schedule of Procedures

	Screen	Subjects Resident in Clinical Research Unit												FU Tel Call				
		Day	-28 to -1	-1	Day 1								2	3*	Day 8 ± 2			
Hour					0	0.25	0.5	0.75	1	1.5	2	4	6	9	12	24	36	48
Informed Consent	X																	
Eligibility Assessment	X	X																
Demographics	X																	
Admission to CRU																		
Randomization																		
Medical History																		
Physical Exam ¹																		
Height, Weight, BMI																		
Weight																		
Resting 12-lead ECG ²																		
Vital signs (BP, PR, RR, Oral Temp)																		
Clinical laboratory tests ³																		
HIV, Hep B&C screen																		
Drug/alcohol screen																		
Pregnancy test ⁴																		
FSH and estradiol ⁵																		
Dose administration ⁶																		
PK blood samples																		
Injection site assessment																		
AE & ConMeds																		
Discharge from CRU																		

NOTE: all timed procedures are with respect to START of study drug infusion.

AE= adverse event; BP = blood pressure; con med = concomitant medications; CRU = clinical research unit; ECG = electrocardiogram; FU = Follow-up; HIV = human immunodeficiency virus; Hep = Hepatitis; PR = pulse rate; PK = pharmacokinetics; RR = respiratory rate.

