13.2 Adverse Events

Adverse events will be recorded beginning immediately after the Informed Consent Form (ICF) is signed. Subjects will be instructed to report AEs during the study and staff will query subjects regarding AEs throughout the study. The Investigator (and/or designee) must document all AEs reported by the subject from the time subjects give consent through the follow-up/completion visit. Any subject who is withdrawn from the study due to an AE shall be followed until the event has resolved or stabilized, and the Investigator will document available follow-up information on the subject's source documentation and eCRF.

13.2.1 *Definitions of Adverse Events*

An AE is any unfavorable and unintended sign, symptom, or disease temporally associated with the use of medicinal (investigational) product, whether or not related to the medicinal (investigational) product. An AE is any symptom, sign, illness, or experience that develops or

worsens in severity during the course of the study. Adverse events reported after consent but before the first dose of study drug are still to be documented by the Investigator but will be considered non-treatment-emergent AEs. Adverse events will be considered treatment-emergent if the onset date is after the first dose of study drug. The severity of each AE will be graded by the Investigator using the National Cancer Institute (NCI) CTCAE v5.0 as follows:

- **Grade 1:** Mild; asymptomatic or mild symptoms; clinical or diagnostic observations only; intervention not indicated;
- **Grade 2:** Moderate; minimal, local, or noninvasive intervention indicated; limiting age appropriate instrumental activities of daily living (ADL);
- **Grade 3:** Severe or medically significant but not immediately life-threatening; hospitalization or prolongation of hospitalization indicated; disabling; limiting self-care ADL;
- **Grade 4:** Life-threatening consequences; urgent intervention indicated;
- **Grade 5:** Death related to AE.

Abnormal results of laboratory tests or diagnostic procedures are considered AEs if the abnormality:

- Is associated with clinical signs or symptoms
- Is considered by the Investigator to be of clinical significance
- Results in study withdrawal
- Fulfills any of the criteria for a serious AE (SAE), as described in this section
- Requires treatment

An SAE is any untoward medical occurrence at any dose that:

- Results in death
- Is life threatening

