## **6.2 Adverse Events**

All AEs (serious and non-serious) will be collected from the start of signing the ICF and until 30 days after the administration of the study drug. All reported AEs will be coded using Medical Dictionary for Regulatory Activities Version 24.0 or higher. All AEs will be graded using National Cancer Institute Common Terminology Criteria for Adverse Events (NCI CTCAE v5.0) refer to the protocol for further information. The causal relationship to study drug will be specified as Related, Probably Related, Probably not related, Not Related. For serious adverse events (SAE) that occur at any time following post dosing or end of the study and there is a reasonable possibility that the SAE is related to the study drug by the Investigator it must be promptly reported to the Sponsor. The incidence of treatment-emergent AEs (TEAE) – events with onset dates on or after the first dose date of the study drug and up to 30 days following the last dose of study drug – will be included in incidence tables. Events with missing onset dates will be considered treatment-emergent. All AEs will be summarized by severity and by relationship to study treatment. If a subject experiences more than 1 occurrence of the same AE (preferred term), the occurrence with the greatest severity and with association (Relationship to study treatment = ‘Related’ or ‘Probably Related’) to the study treatment will be used in the summary tables. Serious adverse events and AEs causing discontinuation will be tabulated. Treatment related SAEs and AEs causing discontinuation will also be summarized. All deaths during the study will be summarized and listed. All AEs will be listed by subject, System Organ Class (SOC) and Preferred Term (PT), along with information regarding onset, duration, CTCAE grade v5, and relationship to study treatment, action taken with study treatment, nature of event, and outcome. (Refer to the protocol for further information.) All tabulations will be presented by treatment. All AEs will be listed by subject and by treatment.

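### The by-treatment AE severity and relationship tables are specified on all AEs from consent, not on TEAEs, so pre-dose events of dosed subjects enter them

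*SAP*

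**What the plan says.** Collection starts at consent in both documents. SAP 6.2: "All AEs (serious and non-serious) will be collected from the start of signing the ICF", continuing to 30 days after dosing. Protocol 13.2: "Adverse events will be recorded beginning immediately after the Informed Consent Form (ICF) is signed".

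The protocol separates pre-dose events. Under section 13.2.1, events arising between consent and first dose are recorded, "but will be considered non-treatment-emergent AEs".

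SAP 6.2 makes the same distinction for one set of tables. It defines TEAEs by an onset from the date of first dose up to 30 days after dosing, and assigns them to the incidence tables. The breakdown that follows has a different subject: "All AEs will be summarized by severity and by relationship to study treatment". The section then says that every tabulation is by treatment. The protocol synopsis matches: "Tabulations will be prepared including all AEs and all AEs by relationship and severity". Protocol 14.7 summarises adverse events by SOC and PT for each treatment and does not mention treatment emergence.

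For a preferred term that recurs in a subject, SAP 6.2 keeps the occurrence that is most severe and associated with treatment. It does not require that occurrence to be post-dose.

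**The concern.** Within one section the SAP uses TEAEs for incidence and all AEs for severity and relationship. Screening runs for up to 28 days and randomization is scheduled on Day 1 (SAP Table 2). A screening event therefore precedes both the dose and the assignment, yet it would be counted in a dose or placebo column.

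AE incidence is a primary endpoint (SAP 2.3), and SAP section 6 bases the safety evaluation on incidence, severity and relatedness. As specified, only the first of these is restricted to treatment-emergent events. Three things follow:

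- Severity counts, and the total and Not related row of the relationship table, carry background that cannot be due to the drug.
- The three tables need not reconcile.
- For a given preferred term, a worse screening occurrence could stand in for a milder post-dose one.

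**Working it through.** **Event set, table by table (SAP 6.2)**

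| Output | Event set stated | Pre-dose AEs of dosed subjects |
|---|---|---|
| Incidence tables | TEAEs | Out |
| Severity and relationship summaries | All AEs | In |
| SAE and discontinuation tables | None stated | Not settled |
| Listings | All AEs | In, as they should be |

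SAP section 6 bases safety summaries on the Safety Population, so screen failures and other undosed subjects contribute nothing.

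**Length of the pre-dose window.** Protocol 8.1 gives a screening period of up to 28 days, a call on Day 8 ± 2, and participation of up to about 38 days. Check: 28 + 8 + 2 = 38, which agrees. The 28 days is a maximum per subject.

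**Illustrative share of background AEs that are pre-dose.** The documents give no AE rate. Assume a constant daily rate, so that share = pre / (pre + post). The post-dose length depends on the source: 30 days in SAP 6.2, or 7 days from Day 1 to the Day 8 call in the protocol.

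| Pre-dose days | Post-dose 30 days | Post-dose 7 days |
|---|---|---|
| 7 | 7/37 = 19% | 7/14 = 50% |
| 14 | 14/44 = 32% | 14/21 = 67% |
| 28 | 28/58 = 48% | 28/35 = 80% |

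**Effect of one subject.** A subject whose only AE is pre-dose moves a dose column by 1/6 = 17 percentage points, or pooled placebo (4 cohorts × 2 = 8 subjects) by 1/8 = 12.5 points.

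**Chance that it happens at all.** If a proportion q of dosed subjects has a pre-dose AE (assumed), the chance of at least one among 32 is 1 − (1 − q)^32. That gives 48% at q = 2% and 97% at q = 10%.

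**Repeated-event rule.** Take a subject with a Grade 2 headache in screening and a Grade 1 headache after dosing, rated probably related. Severity points to the first and association to the second. The rule does not say which prevails, and nothing in it excludes the pre-dose occurrence.

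**The case against.** The best case for the plan is that the author meant TEAEs throughout. The sentence follows directly on the TEAE definition, and a severity table can be read as an incidence table split by grade. The table shells are a separate document and may already restrict it. This is possible, but the text changes its term within the section and the synopsis repeats the all-AE wording. SAP section 1 has the shells followed once the SAP is signed, so the intention should be stated in the SAP.

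Some stronger readings are tempting, and the documents do not support them:

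- *The SAE and discontinuation tables are also specified on all AEs.* SAP 6.2 does not say so; those sentences give no event set.
- *Drug-related counts are inflated.* Protocol 13.2.1 puts events with no time link to the drug under Not related, so the related rows should not change.
- *Dose differences are hidden.* If background is equal across columns, expected differences in event counts are unchanged; ratios shrink and noise is added. Every AE is also listed with onset and grade, so a pre-dose event can be identified in a study of up to 32 subjects.
- *Dose escalation is affected.* Protocol 10.6 rests escalation on committee review of data through Day 8, not on these final tables.
- *Most tabulated background events would be pre-dose.* The 50% to 80% range needs the 7-day window, and SAP 6.2 itself sets 30 days. The constant rate is also doubtful. Protocol 13.1.5 and SAP section 6 describe laboratory and examination findings as AEs when they arise after dosing. Assessment is intensive after dosing, and no procedure is scheduled between screening and Day -1. Subjects with notable screening events may also be excluded at the Day -1 eligibility check.

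**Conclusion.** The point holds for the severity and relationship summaries. As written, they include pre-dose AEs of dosed subjects and present them by treatment, while the incidence tables exclude them. The expected result is higher severity counts, a larger Not related row, and tables that need not agree with each other. A post-dose occurrence may also be displaced under the repeated-event rule.

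The size cannot be derived from the documents. The illustrative shares rest on an assumed constant rate and on 7 to 28 pre-dose days. They are probably too high under either post-dose window, because capture is heavier after dosing and only dosed subjects count. What needs no rate assumption is the weight of one subject in a column of six.

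This is a modest flaw in the primary safety outputs. It does not threaten the related-event counts or the escalation decisions.

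**What to change.** 1. In SAP 6.2, make TEAEs the subject of the sentence on severity and relationship summaries.
2. State that the repeated-event rule operates within TEAEs, and say whether severity or association decides when they point to different occurrences.
3. List AEs with onset between consent and first dose separately.
4. Keep all SAEs from consent reported, as protocol 13.2.3 requires. State the event set of the SAE tabulation, showing pre-dose SAEs apart from treatment-emergent ones. Simply restricting that table to TEAEs would remove pre-dose SAEs from it.
5. Align the synopsis sentence and protocol 14.7. Protocol section 14 lets the SAP carry changes to the planned analyses; if that route is used, record the change in SAP section 9, which now states that there are none.

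Two small residuals remain. The SAP's TEAE rule works on dates, so Day 1 events before the infusion still count, as do events with a missing onset date. A footnote can say so.

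The cost is a few words in the SAP and synopsis, matching table shells, and one listing. No new data are needed, and the change can be made before unblinding.

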10.6 Dose Adjustment and Stopping Criteria

Dose escalation decisions will be based on safety and tolerability assessments (AEs and results from clinical laboratory tests, physical examination findings, injection site assessments, ECGs, and vital signs), as well as PK analysis of each cohort, and agreed upon by the SMC.

The data to be evaluated will be safety data collected through to Day 8. If for any reason there is not a minimum amount of data available for at least 6 subjects, the site will enroll replacement subjects until the minimum data threshold for dose escalation is met. Replacement numbers will be utilized in order to ensure that the treatment ratio (6:2) is maintained.

AUC limit/cap of 16550 ng•hr/mL (i.e. escalation to the next dose should not proceed if the expected AUC will exceed 16550 ng•hr/mL). The limit is based on the mean AUC of male and female monkeys at the NOAEL (3 mg/kg) in the 28-day toxicity study.

The Common Terminology Criteria for Adverse Events (CTCAE) Version 5 will be used to grade AEs.

The trial stopping criteria (that is no increase in the dosing schedule) will be based on the safety data reviewed by the SMC and agreement prior to higher dosing any additional subjects if:

- Any one Grade ≥ 3 AE unless the AE is clearly and incontrovertibly due to extraneous causes. ;
- Any two Grade ≥ 2 AEs unless the AEs are clearly and incontrovertibly due to extraneous causes
- If a serious AE (SAE) attributed to the study drug is observed, the study will be stopped, and the SMC will review all safety and PK data available up to that point in time. If in this case the SMC recommends dose de-escalation to the previously tolerated dose, or the addition of another cohort at an intermediate dose level below the dose level causing the SAE, before proceeding the Institutional Review Board (IRB) will be notified and must approve restarting the study after reviewing the additional safety measures submitted to the IRB as a protocol amendment.

Grade 3 asymptomatic laboratory abnormalities that resolved to \leq Grade 1 within 3 days may be excluded from the definition of DLT. It should be made clear that these are guidelines only and the Investigator together with the SMC can stop dosing for an individual, a cohort, or the study at any time if considered necessary. In such instances the reasons for stopping should be clearly documented.

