14.7 Safety Analyses

Adverse events will be summarized by system organ class (SOC) and preferred term (PT). A subject will only be counted once per SOC and once per PT within a treatment. Subject counts and percentages and AE counts will be presented for each treatment and totaled for all treatments. Listings will be presented by subject for all AEs.

Clinical laboratory values at each visit and change from baseline will be summarized using descriptive statistics (n, mean, median, standard deviation, minimum, and maximum). All clinical laboratory data will be presented in listings. Within each listing, laboratory values outside the normal ranges will be flagged as either high (H) or low (L).

Other safety parameters will be listed and summarized using descriptive statistics. For vital signs and 12-lead ECGs, values outside the normal ranges will be flagged in the listings and change from baseline will be summarized. No formal statistical analysis of safety data is planned.

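### SAP 6.2 selects one occurrence of a repeated adverse event on severity and relatedness jointly, so either the worst grade or the related event can drop out of a summary table

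*SAP*

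**What the plan says.** SAP 6.2 asks for two kinds of summary: "All AEs will be summarized by severity and by relationship to study treatment". The Protocol synopsis asks for the same: "Tabulations will be prepared including all AEs and all AEs by relationship and severity". That wording allows either separate tables or a cross-table.

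Relationship has four levels: "The causal relationship to study drug will be specified as Related, Probably Related, Probably not related, Not Related". The first two count as associated.

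For a preferred term that occurs more than once in a subject, SAP 6.2 reduces the occurrences to one record, "the occurrence with the greatest severity and with association", and sends that record to the summary tables in general. It does not say which condition yields when they conflict, what to do when no occurrence is associated, or how to assign a grade or relationship at SOC level.

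Protocol 14.7 gives a counting rule only: "A subject will only be counted once per SOC and once per PT within a treatment". It does not say which occurrence supplies the grade or the relationship.

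**The concern.** A severity table and a relationship table ask different questions of the same subject: how bad was the worst event, and was any event attributed to the drug. One record answers both only if the worst occurrence is also an associated one. When it is not, the SAP's two conditions point to different records, and two programmers following the text could produce different tables.

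Safety is the primary objective. SAP section 6 bases the safety evaluation on incidence, severity and relatedness, and Protocol 14.7 plans no formal testing of safety data. The descriptive tables are therefore the summarised safety result. In dose cohorts of 6 active subjects, one wrongly placed subject is visible in a percentage.

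**Working it through.** The plan gives no figure to reproduce, because this is a counting rule. The check lists every case the rule can meet when a preferred term occurs twice in one subject.

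**Inputs.** CTCAE grades 1 to 5 (Protocol 13.2.1). Four relationship levels, two of them associated (SAP 6.2). Six active and two placebo subjects per cohort, up to four cohorts (Protocol 8.1). Placebo subjects pooled in summaries (Protocol 14).

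**Patterns.**
- Occurrence types: 5 grades × 4 relationship levels = 20.
- Unordered pairs, repeats allowed: 20 × 21 / 2 = 210.
- Conflict (higher grade not associated, lower grade associated): 10 pairs of different grades × 2 non-associated levels × 2 associated levels = 40, or 40/210 = 19%.
- No associated occurrence: 10 non-associated types, so 10 × 11 / 2 = 55.
- With grades 1 to 3 only: 12 types, 12 × 13 / 2 = 78 pairs; conflict 3 × 2 × 2 = 12; none associated 6 × 7 / 2 = 21.

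**What each single-record reading does** (210 patterns; where none is associated, the worst occurrence is assumed as the fallback, which the SAP does not state):

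| Selection | Worst grade hidden | Related event lost |
|---|---|---|
| Association first, then highest grade | 40 | 0 |
| Highest grade first, association breaks ties | 0 | 40 |
| Separate selection for each table | 0 | 0 |

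**Example.** A subject has a Grade 3 Not Related and a Grade 1 Related occurrence of the same term.
- Association first: the record is Grade 1 Related. The severity table shows Grade 1, two grades below the worst.
- Severity first: the record is Grade 3 Not Related. The relationship table shows no related event for this term.
- Separate selections: Grade 3 in the severity table, Related in the relationship table, and Grade 1 in a related-by-severity table. All three are true.

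**Weight of one subject.** Active cohort: 1/6 = 16.7 percentage points. Pooled placebo at full enrolment: 4 × 2 = 8 subjects, so 1/8 = 12.5 points.

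**The case against.** The strongest reply is that the sentence has a harmless reading. Severity is named first, so association may be meant only to break ties, and then no worst grade is hidden. This is a fair reading, but it moves the error to the relationship table, where the related milder event disappears. Neither single-record reading serves both tables. The table shells, which are not among the documents, might settle the intent, but the SAP text does not.

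Several limits on the impact stand. SAP 6.2 lists every adverse event with its grade and relationship, and tabulates serious events and those causing discontinuation separately. With at most 32 subjects, a discrepancy can be traced. The trigger needs the same term to recur in one subject after a single infusion, with discordant causality and the non-associated occurrence the more severe. The documents give no basis for estimating how often that would happen.

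Three stronger inferences are tempting, and the documents do not support them.
- *The rule creates a related high-grade event that never occurred.* The SAP selects an occurrence, so grade and relationship come from the same real event. An invented combination (Grade 3 Related in the example) would require taking the two attributes from different records, which the text does not instruct.
- *The primary endpoint is misreported.* SAP 2.3 names the incidence of adverse events and serious adverse events. Under either priority order, the choice of occurrence does not change whether a subject is counted for a term.
- *The tables could mislead escalation.* Protocol 10.6 and 10.7 rest escalation on the committee's review of each cohort's data, not on these final tables. The grade-based criteria also screen for cause: a Grade 3 or higher event counts "unless the AE is clearly and incontrovertibly due to extraneous causes". A final severity table might not display an event the committee weighed, but it would not have informed the decision.

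**Conclusion.** The concern holds in a limited form. SAP 6.2 states a joint selection rule that cannot be met in 40 of 210 two-occurrence patterns because the worst occurrence is not the associated one. Whichever condition is given priority, one of the two summaries is then wrong. In a further 55 patterns the literal rule selects no record, although falling back on the worst occurrence is an obvious repair.

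The effect is confined to the severity and relationship summary tables. The shift of 1/6 is the weight of one active subject in a full cohort, and the pattern counts are not probabilities; neither estimates an expected effect. The conclusion assumes that the table shells do not override the sentence. It is worth correcting because the rule as written misreports in identifiable cases, and a reader should not need the listings to correct a summary table.

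**What to change.** Replace the repeated-event sentence in SAP 6.2 with separate selections, each applied per subject at preferred-term level and again at SOC level:

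- **Severity table:** highest CTCAE grade over all occurrences, regardless of relationship.
- **Relationship table:** strongest relationship over all occurrences, regardless of grade.
- **Any related-by-severity table:** highest grade among the Related or Probably Related occurrences only.

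The first two selections always return a value, so the case with no associated occurrence needs no special fallback. The third correctly leaves out subjects with no related occurrence. The cost is a sentence or two in the SAP and matching footnotes in the shells. No new data are needed.
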